## 2.2 BACKGROUND

AG-86893 is a reformulation of an oral drug, nintedanib (marketed as Ofev®, indicated for the treatment of idiopathic pulmonary fibrosis and non-small cell lung cancer), that binds and inhibits the tyrosine kinase found on VEGFR 1-3, PDGFR $\alpha$  and  $\beta$ , and fibroblast growth factor receptor (FGFR) 1-3 [23]. AG-86893 binds competitively to the adenosine triphosphate binding pocket of these receptors and blocks the intracellular signaling that is crucial for the proliferation, migration, and survival of endothelial cells as well as perivascular cells (pericytes and vascular smooth muscle cells), and for the proliferation, migration, and transformation of fibroblasts [25, 26]. As such, AG-86893 is expected to be effective in inhibiting neovascularization and fibrosis.

### Non-clinical AG-86893 studies

The efficacy of topical ophthalmic administrations of AG-86893 was demonstrated in animal models of corneal neovascularization. Rabbits, whose corneas were sutured with silk threads to induce new blood vessel growth, were given topical eye drops, TID for 14 days following suturing (preventative model) or for 7 days after new blood vessels had grown (remedial model). In both studies, AG-86893 was able to inhibit and regress blood vessels at the doses tested (0.1%, 0.3%, and 1%).

Following a single drop of 0.1% AG-86893 to rabbit eyes, AG-86893 absorbed well into target tissues, with a maximum plasma concentration ( $C_{max}$ ) of 821 ng/g in the cornea and 1000 ng/g in the conjunctiva. These concentrations were at least 23 times higher than the half-maximal inhibitory concentration ( $IC_{50}$ ) values for VEGFR and PDGFR. AG-86893 eliminated from cornea and conjunctiva with a half-life ( $T_{1/2}$ ) of 9 to 13 hours. AG-86893 was well tolerated in rabbits dosed four times daily (QID) to both eyes for 7 days at 0.3%, 0.6%, and 1% dose strengths, and three times daily (TID) to both eyes in rabbits and monkeys for 28 days. The one-month Good Laboratory Practice (GLP) ocular toxicology studies in rabbits and monkeys dosed with 0.3%, 0.6%, and 1% dose strengths, given to both eyes TID for 28 days showed no mortality or drug-related effects, and ocular histopathology examinations showed no adverse effects related to the study drug. The NOAEL dose was identified as 1% TID in both rabbit and monkey.

At the proposed highest clinical dose of 0.3%, the daily area-under-the-plasma concentration-time curve ( $AUC_{0-24hr}$ ) on Day 28 in rabbits and monkeys were 33.0 ng•hr/mL and 3.48 ng•hr/mL, respectively. These values are at least 10 and 98 times lower, respectively, than that observed ( $AUC_{0-24hr}$  of 342 ng•hr/mL) in humans with the reference listed drug (RLD) after oral dosing of 150 mg twice daily for 28 days, which showed no dose-limiting toxicities [27]. The safety margin increases to 20 to 196-fold, when taking into account that the planned human study will dose only 1 eye.

Refer to the Investigator's Brochure [28] for details on these non-clinical studies.

### Pharmacokinetic nintedanib studies

*Absorption:* Nintedanib reached  $C_{max}$  between 1 and 4 hours following 150 mg oral doses of capsules (Table 2-1, Table 2-2, and Table 2-3). The oral bioavailability of nintedanib in humans is roughly 5%. Exposures increased by approximately 20% in fed conditions [23].

**Table 2-1 Pharmacokinetic Parameters Following Twice Daily Oral Dosing of Nintedanib for 14 Days to Patients With Idiopathic Pulmonary Fibrosis**

Dose	N	$C_{max,ss}$ (ng/mL)	$AUC_{\tau,ss}$ (ng•hr/mL)	$T_{max,ss}$ (hr)	$T_{1/2}$ (hr)
BID x 14 days					
100	4	20.0	115	3.4	23.4
150	9	39.7	218	3.9	27.5

$AUC_{\tau,ss}$ , area under the plasma concentration-time curve at steady state over a uniform dosing interval tau; BID, twice daily;  $C_{max,ss}$ , maximum plasma concentration at steady-state;  $T_{1/2}$ , half-life;  $T_{max,ss}$ , time to reach maximum plasma concentration at steady-state.

Source: Ogura et. al., 2015 [30]

**Table 2-2 Pharmacokinetic Parameters Following Once Daily or Twice Daily Oral Dosing for 29 Days of Nintedanib in Patients With Solid Tumors**

Dose	N	$C_{max,ss}$ (ng/mL)	$AUC_{\tau,ss}$ (ng•hr/mL)	$T_{max,ss}$ (hr)	$T_{1/2}$ (hr)
QD x 29 days					
50	1	8.22	32.1	3.07	14.7
100	1	40.8	207	2.00	11.8
200	8	35.4	223	1.98	15.3
250	6	58.6	479	2.53	13.7
300	3	50.5	482	3.00	14.1
BID x 29 days					
150	6	34.8	171	1.03	16.3
150 + 200	6	48.0	260	2.13	15.6
200	6	44.9	303	2.72	19.0

Dose	N	C max,ss (ng/mL)	AUC t,ss (ng•hr/mL)	T max,ss (hr)	T 1/2 (hr)
250	11	44.2	226	2.08	16.7
300	3	68.6	366	2.00	12.9

AUCt,ss, area under the plasma concentration-time curve at steady state over a uniform dosing interval tau; BID, twice daily; Cmax,ss, maximum plasma concentration at steady-state; QD, once daily; T1/2, half-life; Tmax,ss, time to reach maximum plasma concentration at steady-state.

Source: Mross et.al, 2010 [27]

**Distribution:** In humans, the volume of distribution following an intravenous dose was 1050 L and was highly protein bound (serum albumin). Nintedanib is preferentially distributed into plasma [23]

**Metabolism:** As with the animal species, the major metabolite of nintedanib is the hydrolytic cleavage product, BIBF 1202 (free acid), and its glucuronide. Minimal cytochrome P450-dependent metabolites were found in human plasma. The major metabolites were not considered active at clinically relevant concentrations [23, 31].

**Table 2-3 Pharmacokinetic Parameters of Nintedanib and Its Metabolites Following a Single Oral 100 mg Dose of Nintedanib to Healthy Volunteers**

Analyte	N	C max (ng/mL)	AUC (ng•hr/mL)	T max (hr)	T 1/2 (hr)
Single Dose					
Nintedanib	12	8.4	56.2	3.0	11.7
BIBF 1202	10	5.7	42.4	5.0	3.2
BIBF 1202 glucuronide	12	11.1	630	10.0	36.8

AUC, area under the plasma concentration-time curve; Cmax, maximum plasma concentration; T1/2, half-life; Tmax, time to reach maximum plasma concentration.

Source: Dallinger et. al, 2016 [32]

Following a 100-mg dose of C-nintedanib in humans, BIBF 1202 free acid and its glucuronide accounted for 32% and 47% of total radioactivity [23, 31].

**Elimination:** Total plasma clearance of nintedanib was 1390 mL/min, with over 90% of the drug excreted in feces/biliary excretion. The plasma T1/2 was between 10 and 15 hours [23, 31].

## 2.3 RISK/BENEFIT ASSESSMENT

### 2.3.1 KNOWN POTENTIAL RISKS

Risks of long-term (52-week) orally dosed nintedanib are described in the Ofev package insert and summarized in the AG-86893 Investigator's Brochure [28]. In brief, there was a dose-dependent increase in liver enzyme levels in patients. Liver enzyme increases were reversible with dose modification or discontinuation and were not associated with clinical signs or symptoms of liver injury. The most common side effects were gastrointestinal irritation (diarrhea, nausea, abdominal pain, vomiting, and decreased appetite), headache, weight decrease, and hypertension [33]. As with most anti-VEGF therapies, arterial thromboembolic events have been reported.

For AG-86893, the risk to the participant is expected to be low. In this study, the highest proposed dose of 0.3% given TID will expose participants to 0.36 mg of nintedanib per day (3 mg/mL x 0.040 mL x 3), which is over 800 times less than what has been approved for the RLD (300 mg; 150 mg

BID). Furthermore, the duration of treatment (28 days) is similar to the above Phase 1 study, in which no dose-limiting toxicities were observed at the 150 mg BID dose [27].

### 2.3.2 KNOWN POTENTIAL BENEFITS

The commercial product (Ofev®; nintedanib ethanesulfonate) has been approved for the treatment of idiopathic pulmonary fibrosis due to its antifibrotic mechanism, and for non-small cell lung cancer, due to its antiangiogenic mechanism.

For AG-86893, there is potential for the reduction of conjunctival hyperemia with short-term use, as well as reduction of new blood vessel growth and fibrosis that may contribute to the growth of the pterygium with longer-term use.

### 2.3.3 ASSESSMENT OF POTENTIAL RISKS AND BENEFITS

This study incorporates standard laboratory assessments as well as general and ocular examinations to detect risk to participants. Because the potential systemic and ocular risks to 4 weeks' exposure of AG-86893 are readily detectable and limited, the opportunity to assess the potential benefit for an unmet need is justified.

## 3 OBJECTIVES AND ENDPOINTS

OBJECTIVES	ENDPOINTS	JUSTIFICATION FOR ENDPOINTS
Safety		

 
Evaluate the safety and tolerability of topical eye drops of AG-86893 in participants with pterygium
 
	
 
Changes in findings detected by vital sign assessment, laboratory tests, ECG
 
Changes in findings detected by BCVA testing, biomicroscopy, TFBUT, lissamine green conjunctival staining, ophthalmoscopy
 
Adverse events
 
Participant assessment of ocular symptoms via questionnaire, including eye dryness, burning/stinging, itching, foreign body sensation, eye discomfort, photophobia, and ocular pain
 
	
 
These tests are standard investigations of general systemic health
 
These tests comprise a standard eye examination to investigate ocular health
 
Severity and causality of AEs are standard endpoints
 
Because pterygia may be associated with ocular symptoms, it will be important to investigate whether treatment has any effect on these symptoms
 

Efficacy		

 
Evaluate the dose response of AG-86893 on conjunctival hyperemia
 
	
 
Change from baseline in overall conjunctival hyperemia score at Day 28 (primary efficacy endpoint)
 
Change from baseline in overall conjunctival hyperemia score at Day 7 and Day 56 (secondary efficacy endpoint)
 
Change from baseline in conjunctival hyperemia score in the quadrant with the
 
	
 
Red eye (e.g. Conjunctival hyperemia) is a chief complaint in participants with pterygia. The assessment will be done as a sum of all 4 quadrants to ensure appropriate benefit: risk (i.e., no increase in hyperemia in one quadrant, while decrease in quadrant with pterygium)
 
This will be assessed to differentiate overall conjunctival
 

OBJECTIVES	ENDPOINTS	JUSTIFICATION FOR ENDPOINTS
	pterygium at Days 7, 28 and 56 (secondary efficacy endpoint)	hyperemia from that of the quadrant with the pterygium
Pharmacokinetic		

 
Determine plasma concentrations of AG-86893
 
	
 
Plasma concentrations of AG-86893
 
	
 
Plasma concentrations of AG-86893 will be monitored to evaluate the amount of systemic exposure following ocular dosing
 

Exploratory		

 
Evaluate the dose response of AG-86893 on pterygium vascularity
 
Evaluate the dose response of AG-86893 on pterygium volume
 
Evaluate the dose-response of AG-86893 on pterygium vessel length
 
	
 
Change from baseline in pterygium vascularity at Days 7, 28 and 56
 
Change from baseline in pterygium volume, as assessed by AS-OCT, at Days 7, 28 and 56
 
Change from baseline in pterygium vessel length at Days 7, 28 and 56
 
	
 
Pterygium vascularity is a known factor to affect hyperemia
 
While the ultimate goal of treatment is to reduce the volume of the pterygium lesion, this is likely to only be accomplished with longer dosing than what is provided in this study
 
Findings from a rabbit corneal neovascularization study demonstrated regression of vessel length in the pterygia over 7 days of treatment
 

AS-OCT, anterior-segment optical coherence tomography; BCVA, best-corrected visual acuity; ECG, electrocardiogram; TFBUT, tear film break-up time.

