#### 8.1.1 PRIMARY EFFICACY MEASURE

- **Overall conjunctival hyperemia.** Digital slit-lamp photos will be captured and submitted to the central reading center for assessment. Conjunctival hyperemia will be measured in 4 quadrants of the ocular surface and graded using a 5-point scale of 0 = none, 1 = mild, 2 = moderate, 3 = severe, and 4 = very severe. The overall conjunctival hyperemia is the average of the score of each quadrant

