#### 8.1.2 SECONDARY EFFICACY MEASURE

- **Localized pterygium conjunctival hyperemia.** Using the above digital slit-lamp photos and grading, the localized pterygium conjunctival hyperemia is the score of the quadrant with the pterygium as assessed by the central reading center.

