#### 9.4.2 ANALYSIS OF THE PRIMARY EFFICACY ENDPOINT

The primary efficacy measure is overall conjunctival hyperemia score of the study eye using the average of the scores of each quadrant, as assessed by the reading center. The primary endpoint is the change from baseline in overall conjunctival hyperemia score at Day 28, so scores from Days 1 and 28 will be analyzed. The primary efficacy analysis will be based on the mITT population. Refer to the MOP for details on the collection of ocular photography.

Statistical analyses will be performed as described in [Section 9.4.1](#) for continuous variables.

---

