4.3 Primary Efficacy Endpoints

The primary efficacy measure is the overall conjunctival hyperemia score graded by the masked reading center and defined as the average of the scores of each quadrant. The primary efficacy endpoint is the change from baseline in overall conjunctival hyperemia score at Day 28.

The primary efficacy analysis will be based on the modified intent-to-treat (mITT) population.

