6.5.2 Secondary and Exploratory Variables and Sub-Study Variables

Secondary, exploratory and exploratory sub-study numerical endpoints will be explored using the same approach as outlined for the primary efficacy analysis and might include the following:

- Change from baseline in conjunctival hyperemia score at the study quadrant at Days 28
- Change from baseline in pterygium vascularity at Days 28 and 56

- Change from baseline in pterygium vessel length at Days 28 and 56
- Change from baseline in Pterygium volume at Days 28 and 56
- IOP
- BCVA in letters read correctly
- Biomicroscopy parameters for conjunctiva, cornea, and iris. Lens status scale
- TFBUT
- Lissamine green conjunctival staining score
- Fundus
- Participant questionnaire

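### Section 3 justifies the four-quadrant primary score as ensuring that no other quadrant reddens while the pterygium quadrant improves, but a sum or average is a net score and cannot show this, and no supplied analysis does.

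*Protocol*

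**What the plan says.** The justification column of the table in Protocol Section 3 gives the reason for scoring all four quadrants: "The assessment will be done as a sum of all 4 quadrants to ensure appropriate benefit: risk (i.e., no increase in hyperemia". The rest of that sentence makes clear that the pattern to be excluded is a rise elsewhere on the eye accompanying a fall at the lesion.

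The definitions of the score read differently. Each quadrant is "graded using a 5-point scale of 0 = none, 1 = mild, 2 = moderate, 3 = severe, and 4 = very severe" (Protocol 8.1.1), and "The overall conjunctival hyperemia is the average of the score of each quadrant". Protocol 9.4.2 describes the primary measure "using the average of the scores of each quadrant, as assessed by the reading center". SAP 3.1.1 also uses an average, and SAP 4.3 has it "defined as the average of the scores of each quadrant".

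One other hyperemia endpoint works at quadrant level: "the localized pterygium conjunctival hyperemia is the score of the quadrant with the pterygium" (Protocol 8.1.2). The SAP carries it as a secondary endpoint in 4.4 and lists it for analysis in 6.5.2: "Change from baseline in conjunctival hyperemia score at the study quadrant at Days 28". Section 3 says this endpoint is there to distinguish overall hyperemia from hyperemia in the pterygium quadrant.

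**The concern.** Section 3 sets a specific benefit:risk question: does redness appear elsewhere on the eye while the lesion quadrant improves? It then says that the primary score answers it. A sum or an average lets a fall in one quadrant pay for a rise in another, so an improved score is compatible with the very pattern that it is said to rule out.

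The trial is meant to help choose a dose for further study (Protocol 4.2). If the primary result is positive, the Section 3 rationale invites the conclusion that no other quadrant worsened. Neither the primary endpoint nor any analysis in the supplied documents could support that conclusion, although the reading center grades all four quadrants.

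**Working it through.** **The plan's own figure.** Protocol 9.2 assumes SD 1.0, a difference of 1, 20 per group and a 95% confidence level, and states at least 90% power. A one-way ANOVA F-test with group means (0,0,1) has noncentrality 20 × [(1/3)² + (1/3)² + (2/3)²] = 13.33 on 2 and 57 degrees of freedom, which gives power 0.8997. The figure reproduces and is not in dispute.

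**Netting.** Let P be the change in the pterygium quadrant and S the total change in the other three. Then:

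- change in sum = P + S
- change in average = (P + S)/4

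Take a baseline of (3,1,1,1), pterygium quadrant first. This eye meets the hyperemia part of inclusion criterion 7 (at least 2 in the pterygium quadrant, at least 1 in two others).

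| Quadrant changes | Change in sum | Change in average | What happened elsewhere |
|---|---|---|---|
| (−2, 0, 0, 0) | −2 | −0.50 | nothing |
| (−2, +1, 0, 0) | −1 | −0.25 | one quadrant redder, still scored as improvement |
| (−3, +1, 0, 0) | −2 | −0.50 | one quadrant redder, same score as the first row |
| (−2, +1, +1, 0) | 0 | 0 | two quadrants redder, scored as no change |
| (−2, +1, +1, +1) | +1 | +0.25 | three quadrants redder, scored as worsening |

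Rows 1 and 3 show that the score cannot tell a clean improvement from the pattern Section 3 wants excluded. Rows 2, 4 and 5 show that it does penalise reddening elsewhere.

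**When net reddening can be hidden.** Write k = −P for the fall in the pterygium quadrant. The score improves when S < k.

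- If k = 1, improvement needs S ≤ 0. A single quadrant may redden, but only if another non-pterygium quadrant fades at least as much.
- If k = 2 or more, S can be as high as k − 1 and the score still improves. Net reddening elsewhere is then compatible with an improved score.

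**What the other planned outputs add.** The mean change in the other three quadrants follows from the two Day 28 endpoints as (4 × overall change − pterygium change)/3:

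- row 1: (4 × −0.50 + 2)/3 = 0
- row 2: (4 × −0.25 + 2)/3 = +0.33
- row 3: (4 × −0.50 + 3)/3 = +0.33

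This separates rows 1 and 3, but the supplied SAP does not plan it. It can also net within the three quadrants: changes (−2, +1, −1, 0) give (4 × −0.50 + 2)/3 = 0 although one quadrant reddened. A count of participants with any worsened quadrant is needed as well.

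**Sum or average.** Sum = 4 × average for every eye, so the standardised effect and p-value are identical. Only fixed cut-offs change meaning. For example, grades of 2,1,1,0 give a sum of 4 and an average of 1.0; against the overall score of at least 2 in Protocol 4.1, the eye passes on the first scale and fails on the second. The phrase mean overall hyperemia score in Protocol 9.2 fits the average.

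**The case against.** The strongest reply has four parts.

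1. *The score does much of what Section 3 wants.* Reddening elsewhere shrinks the apparent benefit, and for a 1-grade lesion response any net reddening elsewhere removes the improvement altogether. This stands. The fault is in the claim to ensure absence, and in larger lesion responses.

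2. *Redness is captured in other ways.* The protocol lists the overall score at Days 7 and 56. The questionnaire records redness of the study eye (SAP 3.1.6, 6.8), biomicroscopy grades the conjunctiva (SAP 3.1.4, 6.5.2), and ocular inflammation is an event of special interest (SAP 4.7.1). This also stands, but none of these is reported by quadrant.

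3. *The two Day 28 endpoints together already determine the mean of the other three quadrants.* That is true for arm means, but the supplied SAP does not plan the calculation and it misses a single worsening quadrant. Tables and listings are specified in SAP Module II, which was not supplied, so a quadrant table there cannot be excluded.

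4. *This is an exploratory trial of about 20 per arm, and no decision rule rests on the Section 3 cell.* That is correct, and it is why descriptive outputs are enough.

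A reader might also infer three stronger things that the documents do not support:

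- *That preservative-induced redness is being hidden.* Benzalkonium chloride is in the vehicle as well as both active strengths (Protocol 6.2.2), so it gives no reason to expect a masked difference between drug and vehicle.
- *That some known share of apparent responders conceals harm.* The documents give no rates of change by quadrant, so no share can be stated.
- *That sum versus average alters the primary test.* It does not, as shown in the working.

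**Conclusion.** The point holds in a limited form. The property that Section 3 claims for the primary score does not exist, whether the score is a sum or an average. This is arithmetic and needs no assumption about the drug. Its size per participant is bounded: a fall of k grades in the pterygium quadrant can hide net reddening elsewhere of up to k − 1 grades in total. Its frequency is unknown.

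The primary endpoint, its test and the sample size are unaffected. What is missing is a planned output that answers the benefit:risk question the protocol itself raises. That conclusion rests on the supplied protocol and SAP, without SAP Module II. The sum/average discrepancy is close to clerical and should be corrected in the same sentence.

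**What to change.** **Protocol Section 3.** Change sum to average, to match Protocol 8.1.1 and 9.4.2 and SAP 3.1.1 and 4.3. Replace the claim that the score ensures no increase in another quadrant with a statement that it is a net measure across the four quadrants.

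**SAP 6.5.2.** Add two descriptive outputs by arm, each compared with vehicle:

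1. Number and percent of participants with an increase of at least 1 grade from Day 1 to Day 28 in any non-pterygium quadrant.
2. Mean change from Day 1 to Day 28 in the average of the three non-pterygium quadrants.

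Output 1 must be read against the vehicle rate, because grading noise alone will produce some increases. As an illustration, assume each of the three quadrants independently rises by chance with probability p. The share flagged in an arm with no drug effect is 1 − (1 − p)³: 27% at p = 0.1, 49% at 0.2 and 66% at 0.3.

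Base the benefit:risk statement on these two outputs, and specify them before the first database lock, after which Day 28 results are presented by unmasked treatment group (SAP 3.4 and 8).

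The cost is one protocol sentence and one SAP table. The grades are already collected, so no new readings or visits are needed.

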## 4 STUDY DESIGN

### 4.1 OVERALL DESIGN

The clinical hypotheses for this study are:

- AG-86893 has an acceptable safety profile, as measured by the incidence and severity of AEs compared with vehicle
- At least 1 concentration of AG-86893 is effective, as measured by the mean change from baseline in overall conjunctival hyperemia compared with vehicle

This will be a Phase 2, multicenter, prospective, randomized, parallel-group, double-masked study evaluating the safety, tolerability, and efficacy of AG-86893 topical eye drops in participants with pterygium who are at least 18 years of age with overall conjunctival hyperemia score  $\geq 2$  in the study eye. A central reading center will assess conjunctival hyperemia from ocular photography at the screening visit to qualify participant eligibility; in addition, the reading center will assess subsequent visits for conjunctival hyperemia, pterygium vascularity, pterygium volume and vessel length in a masked fashion, to determine efficacy.

The study will have 3 treatment groups—vehicle, 0.1% AG-86893, and 0.3% AG-86893—with participants being randomly assigned in a 1:1:1 ratio to study drug. Study drug will be administered only to the selected study eye, until the Day 28 visit. Compliance with the study drug regimen will be estimated by weighing both eye drop bottles at Day 7 (if visit conducted in-clinic) and again at Day 28.

There will be 6 possible clinic visits, including a 14-day screening period (from Day -14 to -2), followed by a treatment/observation period (Day 1, Day 7 [may be conducted as a phone follow-up], and Day 28), and 2 post-treatment follow-up visits for safety monitoring (Day 56 and Day 84).

Collection of anterior-segment optical coherence tomography (AS-OCT) imaging will be done at sites with the requisite equipment and certified by the reading center. Plasma drug monitoring will be done at selected sites with the required facilities.

Primary database lock will occur after all participants exit the study on Day 84. Assessment of safety, tolerability, efficacy, and plasma concentrations of AG-86893 requires participants to participate for 12 weeks from Baseline to Study Exit (Day 84), plus the 2- to 14-day screening period.

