7. Presence of pterygium, extending beyond the limbus, with associated conjunctival hyperemia in the quadrant containing the pterygium of grade  $\geq 2$  at screening, as assessed by the central reading center based on ocular photography using a 5-point scale of 0 = none, 1 = mild, 2 = moderate, 3 = severe, and 4 = very severe, AND a conjunctival hyperemia score of  $\geq 1$  in at least 2 of the remaining quadrants of the same eye at screening (study eye). If both eyes are affected and meet the inclusion criteria, the eye with the higher overall hyperemia score will be used as the study eye. If both eyes are eligible and have the same hyperemia score, the right eye will be selected as the default study eye

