3.4 Randomization and Masking

Eligible participants will be assigned in 1:1:1 ratio into 1 of the 3 treatment groups. A central randomization scheme will be prepared by an unmasked Trial Runners representative and dispensed via an Interactive Web Response System (IWRS). Randomization schedule will be optimized as much as possible to achieve a balanced distribution of treatment assignment by investigational site, baseline hyperemia severity (grade of 2 vs. > 2), and PK participation.

Randomization assignment will occur by site personnel via IWRS once a participant's eligibility is determined by the investigator and confirmed by the central reading center. The IWRS will provide a unique Subject ID to be used in all study documents as the study identifier.

Study drug will be labeled with medication kit numbers, and the IWRS will provide each site with the specific medication kit number(s) for each randomized participant at the time of randomization. Sites will dispense study drug according to the IWRS instructions. Sites will receive the IWRS confirmation notifications for each transaction. All notifications are to be maintained with the study source documents.

Treatment assignment will be masked to the study participants, the investigators, all study-site personnel (with the exception of the unmasked drug administrator), study monitoring personnel, as well as Central Reading Center personnel during the entirety of the study. Day 28 efficacy and safety results based on the 1st database lock will be presented with unmasked treatment group, but no disclosure of treatment assignment at individual participant level.

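### Protocol 4.1 describes entry by an overall hyperemia score of at least 2, inclusion criterion 7 admits an overall score of 1.0, and the severity factor in SAP 3.4 does not name its score

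*Protocol*

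**What the plan says.** **Entry rules.** Protocol 4.1 describes participants "at least 18 years of age with overall conjunctival hyperemia score" of at least 2 in the study eye. Protocol 6.3 says randomization follows once the final entry criteria are confirmed, and gives Section 4.1 as the place to find them. Section 6.1.2 also refers to 4.1 for study entry procedures.

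Inclusion criterion 7 (Protocol 5.1) asks for pterygium "with associated conjunctival hyperemia in the quadrant containing the pterygium of grade" 2 or more, plus a score of 1 or more "in at least 2 of the remaining quadrants of the same eye at screening (study eye"). It sets no minimum for the overall score. The synopsis gives the same quadrant rule.

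**The score.** Each quadrant is graded "using a 5-point scale of 0 = none, 1 = mild, 2 = moderate, 3 = severe, and 4 = very severe". Protocol 8.1.1 states: "The overall conjunctival hyperemia is the average of the score of each quadrant". SAP 4.3 agrees ("defined as the average of the scores of each quadrant"), as do Protocol 9.4.2 and SAP 3.1.1. One place differs: the justification column in Protocol Section 3 says "The assessment will be done as a sum of all 4 quadrants".

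**Randomization.** SAP 3.4 says the schedule will be optimized as far as possible for balance by site, "baseline hyperemia severity (grade of 2 vs. > 2") and PK participation. It does not say whether the severity grade is the pterygium-quadrant score or the overall score. Protocol 6.3 names no balancing factor.

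**Model.** SAP 6.5 says baseline characteristics found significant might be added as covariates. The sample code in SAP Appendix 2 has treatment as its only term.

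**The concern.** The overall score is a defined term and is also the primary efficacy measure. A floor of 2 on it defines a different population from a floor of 2 on one quadrant. Section 4.1 might be taken as background summary, but the cross-reference in 6.3 makes it the place staff are told to look before randomizing.

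The severity factor inherits the ambiguity. Someone working from 4.1 would find that 2 versus above 2 splits the overall score completely. Someone working from criterion 7 would find that it splits the pterygium-quadrant grade completely. These are different variables, and an analyst cannot carry the factor into the model until the plan says which one was used.

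At stake are a consistent definition of who is eligible, and whether a factor chosen for balance can be used in an analysis with about 20 evaluable participants per group.

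**Working it through.** **Inputs**

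- Quadrant scores are whole numbers from 0 to 4 (Protocol 5.1, 8.1.1).
- Criterion 7: pterygium quadrant at least 2, and at least two of the other three quadrants at least 1.
- Overall score = sum of the four quadrants / 4 (Protocol 8.1.1, 9.4.2; SAP 3.1.1, 4.3).
- Section 4.1 floor: overall score at least 2, that is, a quadrant sum of at least 8.
- One quadrant is counted as the pterygium quadrant.

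**Step 1. Does criterion 7 reproduce the floor in 4.1?** It does not. The lowest eligible pattern is 2, 1, 1, 0, and (2+1+1+0)/4 = 1.0. Even a pterygium quadrant at the top grade with 1 in each other quadrant gives (4+1+1+1)/4 = 1.75.

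**Step 2. Patterns that meet criterion 7.** The other three quadrants can be all non-zero (4³ = 64 ways) or have exactly one zero (3 × 4² = 48 ways), so 112 in all. With three possible pterygium grades the total is 3 × 112 = 336.

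| Pterygium grade | Sum of other quadrants giving an average below 2 | Patterns below 2 |
|---|---|---|
| 2 | at most 5 | 40 of 112 |
| 3 | at most 4 | 22 of 112 |
| 4 | at most 3 | 10 of 112 |
| All | | 72 of 336 (21%) |

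**Step 3. The reverse direction.** There are 5⁴ = 625 patterns in total. The distribution of sums is symmetric about 8, and 85 patterns sum to exactly 8. So (625 − 85)/2 + 85 = 355 patterns average at least 2. Those that also meet criterion 7 number 336 − 72 = 264. The remaining 355 − 264 = 91 fail criterion 7; an example is 4 in the pterygium quadrant with 4, 0, 0 elsewhere (average 2.0, only one other quadrant at 1 or more). Neither rule contains the other.

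**Step 4. The sum wording in Section 3.** Under a sum, the lowest total allowed by criterion 7 is 2+1+1+0 = 4. A floor of 2 would never exclude anyone, so this wording does not reconcile the two sections.

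**Step 5. The balancing factor, applied to the 336 patterns.**

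| Score used | Level 2 | Level above 2 | No level |
|---|---|---|---|
| Pterygium-quadrant grade | 112 | 224 | 0 |
| Overall average | 49 | 215 | 72 |

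The 72 without a level are those at 1.0 to 1.75. If the sum were used, all 336 would fall in the upper level and the factor would separate nothing.

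**Step 6. Which reading is the baseline?** Criterion 7 uses the screening photographs. SAP Section 6 defines baseline as the last recording before dosing, which would be Day 1. The schema lists randomization ahead of Day 1 photography, so a Day 1 central reading may not exist when the IWRS needs the factor.

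**Step 7. Cost of a model term.** With 60 evaluable participants, a treatment-only model leaves 60 − 3 = 57 residual degrees of freedom. Adding a two-level factor leaves 56.

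**The case against.** The best defence is that Section 4.1 is narrative, that Section 5.1 is the operative list of criteria, and that the synopsis agrees with it. The reading center qualifies participants from screening photographs, and sites have probably applied criterion 7. On the factor, criterion 7 attaches the word grade to the pterygium quadrant with a floor of 2, so that reading is natural and leaves nobody unclassified. SAP 3.4 also promises only balance as far as possible, not formal strata.

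Much of this stands. The pterygium-quadrant reading is the more plausible, and the gap for overall scores below 2 arises only on the other reading. Two things remain. Protocol 6.3 gives 4.1 the role of entry criteria. And the word grade does not settle the factor: SAP Section 3 selects the study eye by the highest grade of hyperemia where Protocol 5.1 uses the higher overall score.

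A reader might infer from the low entry score that the power statement fails, since a participant entering at 1.0 can improve by at most 1.0, the whole planned difference. The documents do not support that step. They give no baseline distribution, and they call the sample size empirical and the study exploratory. With 20 per group, SD 1 and group means of 0, 0 and 1, the three-group F test has power 0.900, in line with the stated figure. Nor would reconciling 4.1 to criterion 7 change the headroom, because the score of 1.0 comes from criterion 7 itself.

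**Conclusion.** The plan contradicts itself on the entry threshold and leaves a randomization factor undefined. The lowest overall score is 1.0 under criterion 7 against 2 under Section 4.1. The rules disagree on 72 of 336 patterns in one direction and 91 of 355 in the other. This rests on the average as the governing definition, which four sections support and one justification cell contradicts.

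The counts weight every pattern equally. A reader might infer that 21% of participants fall below 2, or a much larger share if the other quadrants are assumed never to exceed 2. The documents support neither: they give no distribution of scores and no such limit. Nor do they show that anyone was wrongly enrolled or randomized without a level, since they do not record which variable the IWRS uses.

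This should be corrected before the primary analysis. It is not evidence that the trial's result is compromised.

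**What to change.** 1. **Entry rule.** Reconcile Protocol 4.1 with inclusion criterion 7 and the synopsis, which agree with each other. Point the cross-reference in 6.3 to Section 5. Bring the sum wording in Section 3 into line with the defined average.
2. **Randomization factor.** Confirm which variable the IWRS already uses and state it in SAP 3.4: which score, screening or Day 1 reading, the study eye, and graded by the reading center. Protocol 2.2 reports 24 participants already dosed, so this records current practice and must not alter the running randomization. If the variable proves to be the overall average, also record how scores below 2 were handled.
3. **Primary model.** Add that factor as a pre-specified term in SAP 6.5 and Appendix 2. This is an addition, since the code now has treatment only. It lets the analysis use a factor the design already balances on, and takes the choice away from a significance check on the data.

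**Cost.** The protocol wording needs sponsor approval and, under the Statement of Compliance, ethics review unless it counts as administrative. The SAP needs a few lines, finalized before the first database lock in SAP Section 8, when the Day 28 primary analysis is run. The analysis gives up one degree of freedom.
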